#### 6. STATISTICAL METHODOLOGY

#### **6.1.** General Considerations:

As this is an extension study, formal statistical analyses will not be performed. All summaries will be descriptive.

Data will be presented in by-patient data listings. The listings will contain study days as described below:

Study day: relative to the first dose of givosiran in this study. The first dose date is designated as Day 1. On treatment study days will be calculated as: evaluation date – first dose date+1. Pre-treatment study days will be calculated as: evaluation date – first dose date.

Continuous variables will be summarized using the following descriptive summary statistics: number of patients (n), mean, standard deviation (SD), median, quartiles (first quartile [Q1], third quartile [Q3]), minimum value, maximum value, and when specified, standard error of the mean (SEM). The precision of the measurement for each continuous variable will be used to determine the number of decimal places to present in tables, figures and derived listings. Minimum and maximum values will be reported with the same precision as the units of measure. The mean, median, SD, quartiles, and SEM will be reported to 1 greater decimal place. Any values that require transformation to standard units (metric or Standard International [SI]) will be converted with the appropriate corresponding precision.

Frequencies and percentages will be presented for categorical and ordinal variables. If there are missing values, the number of missing values will be presented, but without a percentage. Percentages will be based on the number of non-missing values.

For assessments with repeated collection at a given study visit (e.g. electrocardiogram [ECG] parameters), the mean will represent the value at that visit unless otherwise noted.

# **6.2.** Computing Environment

Analysis will be performed using SAS Version 9.4 or higher. Use of other software will be described in the CSR. Analysis Data Model (ADaM) datasets will be prepared using Clinical Data Interchange Standards Consortium (CDISC) Analysis Model Version 2.1 or higher and CDISC ADaM Implementation Guide Version 1.0 or higher.

#### **6.3.** Baseline Definitions

Baseline will be defined as the derived baseline value in the parent study ALN-AS1-001 (Refer to ALN-AS1-001 SAP; dated 29 September 2017).

### 6.4. Study Groups

All tables and figures will be presented by the following study groups:

- Randomized treatment arm in the parent study/Current treatment arm (i.e., column for givosiran/givosiran vs. placebo/givosiran)
- Total (pooling regardless of randomized treatment arm in the parent study)

Summaries of key efficacy (e.g. PD and Clinical Activity) will also include study group:

• Intended Dose Group (i.e., givosiran 2.5 mg/kg monthly in ALN-AS1-002)

The following rules will be used:

- In analyses on PD measurements using the Intended Dose group, summaries at each postbaseline visit will be based on patients who are on 2.5 mg/kg at that visit.
- In analyses on clinical activity assessments (porphyria attacks and hemin use using the Intended Dose group, only events that occur between the first day of dosing and the last day of dosing with the intended dose regimen (2.5 mg/kg once monthly) are included.

An intended dose period will be defined as starting from the first dose of 2.5mg/kg Givosiran monthly.

Summaries of key safety (e.g. AEs) will also include study groups based upon initial dose in ALN-AS1-002:

- Initial dose of 2.5 mg/kg (monthly)
- Initial dose of 5 mg/kg (at any frequency)

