### 7.5.2. Clinical Activity

Clinical activity of ALN-AS1 will be assessed by the number of porphyria attacks and by the number of doses of hemin administered.

Analysis of Clinical Activity will be performed on the Safety Analysis Set.

**Porphyria attacks:** An attack will be defined as any event with preferred term="Porphyria" recorded on Adverse Event eCRF. Attacks which occur within the same date (i.e., end date of attack is the same date as start date of the next attack) will be counted as one attack. When collapsing attacks that occurred on the same date, the following rules will be applied for severity and location:

- 1. Severity will be assigned the maximum severity among the records.
- 2. Location will be assigned 'hospital' if  $\geq 1$  attack with location=hospital. Location will be assigned 'outpatient' if  $\geq 1$  attack with location=outpatient Location will be assigned 'home' if all the records state location=home. Location will be assigned 'other' if all the records state location=other.

The number of porphyria attacks during the treatment period (attacks with start dates on or after date of first dose) will be summarized. Annualized attack rate (AAR) per patient will be calculated as the total number of porphyria attacks divided by the total person-days at risk and multiplied by the total number of days in a year (365.25). Person-days at risk will be defined as: (date patient went off study – date of first dose+1). For an interim snapshot, the person-days will be defined by date of the first dose until the minimum of the date of the interim snapshot cut-off date or date the patient went off study. For calculation of AAR, only records with non-missing start and stop dates will be considered.

Porphyria attacks will be summarized separately in each subgroup:

- 1. Composite attacks: Attacks requiring hospitalization, urgent health care (i.e. outpatient clinic, Emergency Department, etc.) or IV hematin at home.
- 2. Attacks requiring hospitalization
- 3. Attacks requiring urgent health care (i.e. Outpatient)
- 4. Attacks required treatment with IV hematin at home
- 5. Attacks not treated with IV hematin at home
- 6. All attacks

For each subgroup, the total number of events, total person-years (total days/365.25), mean rate (total number of events/total person-years) and SEM will be presented for each study group. The

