SEM will be calculated using Cochran's estimate of SEM for weighted mean [1]. Attacks for each subgroup will display the rates separately for each phase of study: run-in (ALN-AS1-001 study) and treatment phase (ALN-AS1-002). A tabular summary of percentage change (%) in AAR rate from run-in to treatment phase will be also calculated per cohort. In addition, a by-patient listing will summarize the porphyria attacks in each of the subgroups. An exploratory analysis of AAR based on 6 months of givosiran dosing and beyond 6 months may be explored.

In addition, clinical activity will be assessed by duration and severity of attack (mild/moderate/severe). Reduction from run-in period (ALN-AS1-001 study) in composite to all attacks ratios will be assessed.

Hemin: Dosing with hemin will be summarized for doses during the treatment period (hemin start dates on or after the first dose of givosiran in this study). Hemin dosing will be identified as medication with standardized medication terms such as 'hematin', 'haem arginate' or 'hemin'. Annualized rate of hemin dosing will be summarized in the same manner as porphyria attacks (i.e., mean rate, SEM, person-years, total events). For the calculation of annualized rate of hemin, only records with non-missing start and stop dates will be considered. These summaries will also be presented in the same manner (i.e. separately for each cohort displaying results from each phase of study: run-in (ALN-AS1-001 study) and treatment phase (ALN-AS1-002). An exploratory analysis of Annualized rate of hemin dosing based on 6 months of givosiran dosing and beyond 6 months may be explored.

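### Intended Dose Group attack and hemin rates limit the events to the 2.5 mg/kg monthly window but not the person-days, so they read equal to or below a matched rate

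*SAP*

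**What the plan says.** All references are to the SAP version whose section 6.4 names an Intended Dose Group.

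- **Events (section 6.4).** Key efficacy summaries, including clinical activity, are also shown for patients on 2.5 mg/kg monthly. For attacks and hemin use in that group, the SAP includes "only events that occur between the first day of dosing and the last day of dosing with the intended dose regimen".
- **Period (section 6.4).** The section then adds: "An intended dose period will be defined as starting from the first dose of 2.5mg/kg Givosiran monthly". It gives no end to this period and does not connect it to time at risk.
- **Person-days (section 7.5.2).** The rule opens "Person-days at risk will be defined as: (date patient went off study", from which the date of first dose is subtracted and one day added. At an interim snapshot, time runs from first dose "until the minimum of the date of the interim snapshot cut-off date or date the patient went off study".
- **Rate (section 7.5.2).** For each attack category, "mean rate (total number of events/total person-years) and SEM will be presented for each study group". For hemin: "Annualized rate of hemin dosing will be summarized in the same manner as porphyria attacks". On precision: "SEM will be calculated using Cochran's estimate of SEM for weighted mean".
- **Related rules.** Section 2 allows one or more regimen changes and places post-treatment visits at month 39 or 42, after up to 36 months of treatment. Section 6.5 sets a window of up to 28 days from last dose for attack and hemin data in patients who discontinued treatment. It does not mention person-days.

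**The concern.** A rate needs the same days in its numerator and denominator. Here, events stop counting on the last day of intended-regimen dosing, while the only stated clock keeps running to off-study or cut-off. For a patient who reached the intended regimen after starting on another, the clock also begins before any event can count. Those extra days add person-time and no events, so they dilute the rate.

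The dilution falls in the column for the regimen the SAP itself calls intended, and it works in the drug's favour. Section 6.6 says interim results support regulatory activities and publications. The text is also open enough for two programmers to derive different rates: one may apply section 7.5.2 literally, another may restart the clock at the first intended dose, and a third may borrow the 28-day window as an end date.

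**Working it through.** **Direction.** Let E be the events counted under section 6.4, T_window the days from first to last intended dosing day, and T_full the person-days under section 7.5.2.

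- Rate as written = 365.25 × E / T_full
- Matched rate = 365.25 × E / T_window
- Ratio = T_window / T_full

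The window lies inside the full span for every patient, so the ratio is at most 1, both per patient and when days are summed over patients. The same E appears in both rates, so this comparison needs no assumption about how attacks are spread over time. The pooled rate is low by 1 − ΣT_window / ΣT_full.

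**Inputs.** The SAP states no figure to reproduce and gives no switch counts or dates. From section 2: visits at months 39 and 42, and treatment up to 36 months. Assumed: last intended dose L at month 35 or 36, off study O at month 39 or 42, and a share s of patients who switch to the intended regimen at month 12.

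**Single patients.**

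- Never switched: 36/39 = 0.923 to 35/42 = 0.833, so 8–17% low.
- Switch at month 12, clock restarted at the first intended dose: 24/27 = 0.889 to 23/30 = 0.767, so 11–23% low.
- Switch at month 12, section 7.5.2 read literally: 24/39 = 0.615 to 23/42 = 0.548, so 38–45% low. A later switch is worse: at month 18 the ratio is 18/39 = 0.462 to 17/42 = 0.405.

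**Pooled column.** Numerator = (1 − s)L + s(L − 12). Denominator = (1 − s)O + s(O − 12) if the start is re-anchored, or O if read literally.

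| s | Start re-anchored | Low by | Literal first dose | Low by |
|---|---|---|---|---|
| 0 | 36/39 = 0.923 to 35/42 = 0.833 | 8–17% | same | 8–17% |
| 0.25 | 33/36 = 0.917 to 32/39 = 0.821 | 8–18% | 33/39 = 0.846 to 32/42 = 0.762 | 15–24% |
| 0.50 | 30/33 = 0.909 to 29/36 = 0.806 | 9–19% | 30/39 = 0.769 to 29/42 = 0.690 | 23–31% |

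**28-day window applied to events only** (28 days = 0.92 month), never switched, same dates: 36.92/39 = 0.947 to 35.92/42 = 0.855, so 5–14% low.

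**Interim**, never switched, last dose 365.25 days after the first: with cut-off on the last dose date the ratio is 1. With cut-off 30 days later it is 366.25/396.25 = 0.924. The range is 0–8% low.

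**Limit on the direction.** Take an assumed patient on the regimen in months 0–6 and 18–35 at 3 attacks per year, and off it in months 6–18 at 6 per year. The first-to-last-day window also takes in the off-regimen events: 3 × (23/12) + 6 × 1 = 11.75. Over the 35-month window that is 4.03 per year. With section 7.5.2 person-days it is 3.62 (month 39) to 3.36 (month 42). The written rate is below the matched-window rate but above the on-regimen rate of 3. The direction is therefore guaranteed only against the matched window.

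**The case against.** The strongest reply is that the intended dose period in section 6.4 was meant to set the clock. The event window is already fixed by the bullet above it, so the sentence is idle unless it re-anchors time at risk. That is a reasonable reading, and it makes the re-anchored column of the table more plausible than the literal one. It does not close the gap: the period has no end, and 8–19% remains under the assumed dates.

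A more lenient reading also ends the clock 28 days after last dose. With the start re-anchored and events still stopping at the last intended dose, the ratio is 0.95 to 0.98, or 2–5% low. If the 28 days extended events and person-days alike, the two would match. But section 6.5 never mentions person-days and covers only patients who discontinued treatment. Using it for completers is an inference, and the same caution applies to the 5–14% case above.

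The impact is also limited, and this stands. The study has up to 16 patients, and section 6.1 plans no formal analyses. The arm and Total columns are outside the section 6.4 rule. Events and person-years are shown beside the rate. The percentage change in attack rate "from run-in to treatment phase will be also calculated per cohort" is not stated for this group. Table shells sit in a separate document and might settle the derivation, but the SAP states a denominator, and that denominator does not fit the numerator.

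Finally, a strict first-to-last-dose denominator gives a patient with one intended dose a single day at risk, so one attack that day annualises to 365.25 per year. That follows from the section 6.4 event window itself. It is a reason to choose the window with care, not to leave the two parts unmatched.

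**Conclusion.** The point holds and should be fixed. As written, Intended Dose Group attack and hemin rates use a restricted numerator and an unrestricted denominator. They are equal to a matched rate only if every patient starts on the intended regimen and has the last intended dose on the off-study or cut-off date. Otherwise they are lower.

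Under the assumed dates, the most defensible figure for the final column is 8–19% low with the start re-anchored and up to half the patients switching at month 12. The literal text reaches 31% under the same assumptions. An interim rate for patients who never switched is 0–8% low under its own assumed dates. These are illustrative ranges. The real size depends on switch and last-dose dates that the SAP does not give. No error rate or primary conclusion is affected.

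**What to change.** In sections 6.4 and 7.5.2, state that Intended Dose Group person-days for attacks and hemin, at both final and interim analyses, are counted over exactly the days on which that group's events are counted, truncated at the off-study or cut-off date. Specifically:

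- Give the intended dose period an end. The simplest form keeps the existing event window: last intended dose date − first intended dose date + 1.
- State whether the 28-day window in section 6.5 extends this group's window. If it does, apply it to events and person-days alike.
- For a patient who leaves the regimen and returns, sum the on-regimen intervals and exclude both events and days outside them. This also amends the section 6.4 event rule, so it should be written there, with an end for each interval.
- Use the same person-days as the weights in the Cochran SEM.

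The cost is one paragraph of SAP text and one derivation in the analysis datasets, with some extra programming if patients returned to the regimen. The reported rate may become less favourable.

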#### 2. STUDY DESIGN

Study ALN-AS1-002 is an open-label, extension study designed to evaluate the long-term safety, clinical activity of givosiran in patients with AIP. The number of patients included up to 16 patients from Part C in the parent study ALN-AS1-001.

Eligible patients who completed Part C in the parent study either received the same dosing regimen as the pivotal Phase 3 study (e.g. 2.5 mg/kg every month) or had 1 or more dosing regimen changes across studies. The change in dosing regimen for a patient may occur due to emerging data and decisions from the Safety Review Committee (SRC). After a patient has completed 12 months of givosiran administration in this study (6 months in an every month dosing regimen), and where applicable country and local regulations and infrastructure allow, study procedures, including givosiran administration may take place at the patient's home by a healthcare professional. The expected duration of treatment for each patient is up to 36 months (3 years) followed by a post-treatment visits at either month 39/Early Termination visit or month 42.

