### 7.4. Safety Analyses

The primary objective of this study is to evaluate the long-term safety and tolerability of givosiran in patients with AIP. All analyses will use the Safety Analysis Set. All clinical safety

laboratory data collected from the central laboratory will be used to evaluate safety. For summaries of ECG data, these will be performed separately based upon data collected locally and centrally.

**Parameters:** Safety and tolerability assessments for givosiran will include study drug exposure, AEs, clinical laboratory parameters (hematology, serum chemistry, liver function test [LFT], urinalysis, coagulation), vital signs, 12-lead ECGs, concomitant medication, and physical examinations.

**Exposure:** Summaries will include descriptive statistics of the duration of treatment (days) and total number of doses received. Additional summaries of the cumulative number of patients (percentage) that completed study treatment intervals (e.g.  $\ge 1$  day,  $\ge 1$  month,  $\ge 3$  month, etc.) and the number of patients (percentage) that completed study treatment at the latest visit interval will also be displayed. Additionally, cumulative number of doses received at home will be displayed.

The date of the last exposure to study drug is defined as the earliest day of the following dates:

- Last dose date + 27 days
- Analysis cut-off date
- The date of EOS

Duration of exposure (days) is defined as date of the last exposure – date of the first dose +1. Dose interruptions and compliance will not be considered when calculating of duration of exposure.

A separate per-patient exposure listing will be generated to display the dosing regimen in the parent study (ALN-AS1-001) and actual dosing (mg/kg) regimen(s) in this study.

**Adverse Events:** AEs will be coded using the MedDRA coding system (version 21.0 or later) and displayed in tables and data listing by SOC and PT. Patients who report multiple occurrences of the same PT will be classified according to the most related or most severe category. Patients with a missing severity or missing relationship to study drug will be classified to the most related or most severe category.

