Summaries of AEs will consist of events which occur or worsen (including date/time when applicable) after the first dose of givosiran in this study. Note: Porphyria attacks are recorded on the AE eCRF, however they will not be reported as AEs but rather as an endpoint of clinical activity (see section 7.5.2); therefore, the term "AE" excludes porphyria events.

An overview of the frequency (percentage) of AEs including the total number of events will be tabulated (summaries such as but not limited to, the number of patients with at least 1 AE, the number of patients with at least 1 AE related to study drug, the number of patients with at least 1 serious AE [SAE], the number of patients who discontinued study drug to an AE). Separate tabulations will be generated by SOC and PT for all AEs, AEs by maximum severity, related AEs, related AEs by maximum severity, SAEs, discontinuation from study drug due to AEs, interruption due to AEs, and deaths. Patient listings will be generated separately for any patient who died, discontinued from study drug and reported any SAEs.

An additional set of AE outputs will also be generated by study groups defined by the initial dose of givosiran [i.e. Patients with an initial dose of 2.5 mg/kg (monthly) in ALN-AS1-002 and Patients with an initial dose of 5 mg/kg (at any time) in ALN-AS1-002].

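### AEs are tabulated by starting dose only and without person-time, so the dose columns mix regimens if patients change regimen during the study

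*SAP*

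**What the plan says.** The SAP file holds three versions of the plan. Section numbers here refer to the one placed first (VV-CLIN-003053), taken as current.

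- **Grouping of AEs by dose.** Section 6.4: "Summaries of key safety (e.g. AEs) will also include study groups based upon initial dose in ALN-AS1-002". The two columns are 2.5 mg/kg monthly and "Initial dose of 5 mg/kg (at any frequency"). Section 7.4 repeats this: "An additional set of AE outputs will also be generated by study groups defined by the initial dose of givosiran". No other dose-based AE grouping is planned.
- **Measure.** Section 7.4: "An overview of the frequency (percentage) of AEs including the total number of events will be tabulated". No AE rate per unit of exposure is planned. The nearest thing is the share of injections complicated by an injection site reaction.
- **Regimen changes.** Section 2 says that some patients "had 1 or more dosing regimen changes across studies". The per-patient exposure listing in Section 7.4 shows "actual dosing (mg/kg) regimen(s) in this study", so it allows for more than one regimen per patient within this study.
- **Other endpoints.** Section 6.4: "An intended dose period will be defined as starting from the first dose of 2.5mg/kg Givosiran monthly". For PD in that group, "summaries at each postbaseline visit will be based on patients who are on 2.5 mg/kg at that visit". Attacks and hemin use count only between the first and last day of dosing on that regimen. AEs have no such rule.

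**The concern.** Long-term safety is the primary objective, yet the secondary endpoints are read at the dose in force and AEs are not. An AE that starts after a change of regimen stays in the column of the first dose. If patients go from 5 mg/kg to 2.5 mg/kg monthly, two things follow. The 5 mg/kg column becomes a mixture, so it can blur a real difference between regimens. And the AEs those patients have on 2.5 mg/kg monthly appear in no summary of that regimen, although it is the one the plan calls intended. Without person-time, differences in length of follow-up between the columns add a separate distortion. Section 6.6 says interim outputs will support regulatory activities and publications, so these tables are likely to be read for dose-related safety.

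**Working it through.** The plan states no AE rate, switch time or number of switches, so there is no figure of its own to reproduce. What follows is an illustration.

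**Inputs.** From the SAP: treatment up to T = 36 months and up to 16 patients (Section 2). Assumed: constant AE hazard *l* per month on 2.5 mg/kg monthly, hazard R × *l* on 5 mg/kg, and a switch from 5 to 2.5 mg/kg monthly at month *t*.

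**1. Rate ratio between the columns.** The plan does not report this quantity; it isolates the mixing. With equal follow-up:

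- column rate ratio = (R*t* + T − *t*)/T
- share of the 5 mg/kg column's events that arise on 2.5 mg/kg = (T − *t*)/(R*t* + T − *t*)

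With R = 2:

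| Switch month | Column's person-time on 2.5 mg/kg | Column rate ratio | Column's events on 2.5 mg/kg |
|---|---|---|---|
| 3 | 33/36 = 92% | 39/36 = 1.08 | 33/39 = 85% |
| 6 | 30/36 = 83% | 42/36 = 1.17 | 30/42 = 71% |
| 12 | 24/36 = 67% | 48/36 = 1.33 | 24/48 = 50% |

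With R = 3 the ratio is 48/36 = 1.33 (month 6) or 60/36 = 1.67 (month 12). Counting events and person-time by regimen at onset returns R, but only under constant hazards and no carry-over.

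**2. Crude percentages, which the plan does report.** Patients with at least one event: 1 − exp(−*l*T) in the 2.5 mg/kg column and 1 − exp(−*l*(R*t* + T − *t*)) in the 5 mg/kg column. With R = 2 and T = 36 in both:

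- *l* = 0.02, *t* = 6: 1 − exp(−0.72) = 51.3% against 1 − exp(−0.84) = 56.8%, a gap of 5.5 points. On 5 mg/kg throughout: 1 − exp(−1.44) = 76.3%, a gap of 25.0 points.
- *l* = 0.02, *t* = 12: 1 − exp(−0.96) = 61.7%, a gap of 10.4 points.
- *l* = 0.10, *t* = 6: 97.3% against 98.5%, a gap of 1.2 points. Even 5 mg/kg throughout would give only 2.7 points, because both columns saturate.

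**3. Unequal follow-up.** With *l* = 0.02:

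- No dose effect (R = 1): 36 months gives 51.3% and 24 months gives 1 − exp(−0.48) = 38.1%. The gap is 13.2 points in favour of whichever column is followed for less time.
- R = 2, *t* = 6, with 24 months in the 5 mg/kg column and 36 in the other: 1 − exp(−0.60) = 45.1% against 51.3%. The column with the higher hazard shows the lower percentage.

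**4. Resolution.** If the 16 patients split evenly (assumed), one patient is 100/8 = 12.5 points.

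**The case against.** The strongest reply is that the tables do what their labels say. They are titled by initial dose, they form an additional set beside the main tables, everything is descriptive, and there are at most 16 patients. AE data and actual regimens are listed per patient, so onset regimen can be traced by hand. All of that stands. It lowers the importance of the point, but listings do not give a rate and no planned table does.

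Four stronger readings are tempting, and the documents do not support them.

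- *That 5 mg/kg starters did move to 2.5 mg/kg monthly.* No sentence says so. Section 2 speaks of changes across studies, and a change between the parent study and this one puts no AE in the wrong column. The visit-level PD rule and the listing of regimens make switching within this study the natural reading, but its direction, timing and frequency are not given.
- *That a dose signal is necessarily diluted.* Mixing dilutes a true excess on 5 mg/kg, but unequal follow-up can push crude percentages either way. The 5 mg/kg column also pools all dosing frequencies, so its monthly exposure is unknown.
- *That the tables say nothing about 2.5 mg/kg monthly.* Patients who start on that regimen have their own column. What is missing is the experience of patients who reach it later.
- *That a safety rule was wrongly dropped.* Another version in the file (VV-CLIN-002514, Section 6.5) names AEs in its intended-dose rule. A difference between versions is not an error and no reason is given; it shows only that the sponsor once thought the rule workable.

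Regimen at onset has weaknesses too. In patients who step down, 5 mg/kg always comes first, so regimen is confounded with time on study. The same patient can appear in both columns, and effects may carry over after a switch.

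**Conclusion.** The point holds as a gap in the tabulation. The only dose-based AE tables use the first dose in this study, with percentages and event totals but no person-time, while PD, attacks and hemin follow the dose received. If patients change from 5 mg/kg to 2.5 mg/kg monthly, the 5 mg/kg column mixes regimens and AEs on 2.5 mg/kg monthly after the switch reach no summary of that regimen.

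The size cannot be taken from the document. The rate ratio of 1.08 to 1.33 in place of 2 rests on an assumed doubling, constant hazards, 36 months of follow-up and switches at months 3 to 12. On the percentage scale the loss ranges from large to negligible with the AE rate. This is a cheap improvement to the reporting of the primary objective, not a demonstrated bias in a result.

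**What to change.** Add supplementary AE, SAE and AECI summaries by regimen at onset, intended dose period against all other regimens. Give the number of events, patient-years on that regimen and events per patient-year. Use the dosing dates already derived for attacks and hemin, and state where each regimen period ends so that events and patient-years cover the same days. Keep the initial-dose tables as planned.

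Footnote that:

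- events soon after a switch may carry over from the previous regimen;
- regimen is confounded with time on study;
- a patient can appear in both columns;
- with up to 16 patients the comparison is descriptive and supplements the per-patient regimen and AE listings.

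The cost is one extra set of tables from existing dosing and AE dates. No new data are needed, and nothing about dosing or patient management changes.
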